#### 6.4.2.2 **Prescription Dose and Volume**

6.4.2.2.1 The prescribed dose is the dose that the oncologist intends to deliver and is the dose entered into the treatment record. For the purposes of this protocol, the prescribed dose is 50 Gy to the margin of the GTV. The prescription dose must cover at least 90% of the GTV. The volume encompassed with prescription isodose volume should be recorded on the appropriate data form.

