#### 6.4.3 Organs at Risk (OAR)

6.4.3.1 Optic nerve limit. The dosimetry should be constructed so that the optic nerves, chiasm, and proximal optic radiations receive no more than the prescription dose (50 Gy) to any point along the optic pathway. Exceeding this by more than 5% is a major protocol violation.

6.4.3.2 Hippocampi limit. The dosimetry should be constructed so that the hippocampi receive no more than the prescription dose (50 Gy) to any point. Exceeding this by more than 5% is a major protocol violation.

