11.3 Sample Size

11.3.1 **Overview:** The primary goal of this study is to monitor shrinkage in adenoma size and volume following treatment.

11.3.2 **Sample Size Derivation:** The predicted partial or complete response rate (PR+CR) of treated subjects at a follow-up interval of 12 months is the determinant of sample size. A PR + CR rate of 10% or less would be considered insufficiently low for further investigation of this treatment, whereas a PR + CR probability of 50% or higher will be considered worthy of future investigation. If the true PR + CR rate is 50%, a sample size of 10 patients will provide 87% power to detect a significantly higher RTS than 10% with an alpha level of 0.025. To assure an adequate number of evaluable patients, allowing for a small number of patients who would be lost to follow-up or otherwise found non evaluable, a total of up to 12 patients will be enrolled. This analysis applies to both cohorts (those with and without previous radiation therapy)

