**The sample size of this study will not exceed 24 patients.**

11.3.3 There will be an early stopping rule for unexpected toxicity. If at any point during the study more than 1/6 of patients treated to date experience study treatment-related grade 4-5 toxicity of any kind, study enrollment will be suspended. Treatment related events include those related or possibly related to therapy.

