11.5 Analysis Plan

11.5.1 Interim Reports

11.5.1.1 Interim reports will be updated at least every six months until the results of the study are published. In general, the interim reports will contain information about patient accrual rate with projected completion dates of the trial, status of QA review and compliance rate of treatment per protocol, and the frequencies and severity of toxicity.

11.5.1.2 *The Analysis of Tumor Shrinkage:* This analysis will be carried out when each patient has had at least 730 days (i.e., 24 months) of follow-up. The percent change in size and volume of the adenoma will then be calculated by subtracting the post-treatment measurements from the pre-treatment measurements then divided by the pre-treatment measurements and then multiplied by 100. The mean, median and standard deviation of the percent change will be determined.

11.5.1.3 *Estimation of Secondary Endpoints Related to the Efficacy:* Cumulative incidence approach will be used to estimate the progression free survival. For any individual patient, progressive disease (PD) within the treated lesion will be scored as PD for that patient

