**12.2 Procedures**

- 12.2.1 Clinical trials are assessed for safety on a continual basis throughout the life of the trial. All SAE's and any AEs that are unexpected and possibly/likely related to study participation are reported to UTSW IRB through an electronic research system per UTSW IRB guidelines.
- 12.2.2 All clinical trials are reviewed on monthly basis for enrollment. All local SAEs are reviewed by Radiation Oncology DSMC monthly for severity and attribution. For investigator-initiated trials, all SAEs at affiliated institutions are monitored as local SAEs. The principle investigator and study coordinator will present a study treatment summary and SAEs for review. Source documents will be available for the DSMC members during the review. NCI Common Toxicity Criteria Version 4 will be used for grading and attributing adverse events.
- 12.2.3 If the SAE occurs on a multi-institutional clinical trial coordinated by the Radiation Oncology Clinical Research Office, the Clinical Research Manager or primary coordinator ensures that all participating sites are notified of the event and resulting action, within one (1) working day of the determination.
- 12.2.4 Interim Stopping Rules - Stopping for toxicity or efficacy will be related to dose limiting toxicity as described in the statistical section.

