## Appendix VII

### Risks to Subjects

| Procedure  | Risks   | Measures to Minimize Risks   |
|---|--|---|
| History and physical exam (H&P)                             | Discovery of previously unknown condition  | Will be performed by MD and/or nurse practitioner with oncology experience.   |
| MR imaging / CT imaging of the brain                        | Discovery of previously unknown condition/recurrence or progression of pituitary adenoma; discomfort           | Will be performed by nurse/technician with radiology experience   |
| Blood draws (at all study timepoints)                       | Discomfort, bleeding, bruising, dizziness, fainting, infection   | Blood will be drawn by an experienced phlebotomist.   |
| Zubrod Performance status evaluation                        | Discomfort, psychological stress of answering personal questions   | Subjects informed that they may refuse to answer, take a break, or discontinue participation at any time  |
| Neurocognitive evaluation                                   | Discomfort, psychological stress of answering personal questions   | Subjects informed that they may refuse to answer, take a break, or discontinue participation at any time  |
| QOL assessment  | Discomfort, psychological stress of answering personal questions   | Subjects informed that they may refuse to answer, take a break, or discontinue participation at any time  |
| Interstitial seed placement                                 | Hemorrhage, cerebral spinal fluid leak, neurological deficits

Constitutional:
likely: fatigue | Participants will be educated and asked to inform study personnel if encounter symptoms.  |
| FAX transmittal of case report forms (CRFs) to primary site | Loss of privacy  | Sensitive patient information will be blacked-out. CRFs will only be identified by subject initials and unique, study identification number before fax transmittal. |
| Unforeseen risks  | E.g., unpredictable interaction between radiotherapy and concomitant medications                               | Strong encouragement to report any difficulties and keep researchers aware of any change in medications   |

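### The single pooled 1/6 toxicity trigger in section 11.3.3 lets event-free unirradiated patients dilute a toxicity signal in the separately sized re-irradiated cohort

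*Combined protocol and SAP*

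**What the plan says.** The study synopsis divides patients by prior radiotherapy, with up to 12 per cohort and at most 24 in all. After deriving 10 evaluable and up to 12 enrolled patients for response, section 11.3.2 adds: "This analysis applies to both cohorts (those with and without previous radiation therapy").

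The toxicity rule in 11.3.3 names no cohort. Study enrolment is suspended if at any point "more than 1/6 of patients treated to date experience study treatment-related grade 4-5 toxicity of any kind". Related and possibly related events count.

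Section 12.2.4 adds no second boundary: "Stopping for toxicity or efficacy will be related to dose limiting toxicity as described in the statistical section". Other oversight is by judgement. In 12.2.2, "All local SAEs are reviewed by Radiation Oncology DSMC monthly for severity and attribution", with no threshold given. The interim reports in 11.5.1.1 cover accrual, compliance "and the frequencies and severity of toxicity", and do not call for a split by cohort.

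Treatment is the same in both cohorts. In 6.4.2.2, "the prescribed dose is 50 Gy to the margin of the GTV"; in 6.4.3.1, the optic structures are to "receive no more than the prescription dose (50 Gy) to any point along the optic pathway". The hippocampi have the same limit. Neither limit is adjusted for earlier dose.

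**The concern.** The plan treats prior radiotherapy as important enough to ask the response question separately, yet it monitors severe toxicity as if there were one population. Checklist item 7 defines prior treatment as radiotherapy to the central skull base or central brain, the region that is implanted. If either cohort tolerates the implant less well, the re-irradiated one is the natural candidate.

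Under a pooled fraction, each event-free unirradiated patient enlarges the denominator. The number of severe events the re-irradiated cohort can have before enrolment pauses therefore depends on who enrols first, which the documents do not control. Up to 12 of the 24 patients are affected.

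**Working it through.** **Inputs.** From 11.3.3: suspend when events / treated > 1/6 (strict), checked at any point. From the synopsis: 12 + 12 patients. The plan states no operating characteristics for this rule, so there is no figure of its own to reproduce. All toxicity rates below are assumptions.

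**Step 1: what the pooled rule tolerates.** It suspends when 6 × events > patients treated.

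- Alternating accrual, no unirradiated events, k re-irradiated among n = 2k treated: k = 3 gives 1/6, k = 6 gives 2/12, k = 9 gives 3/18. Each equals 1/6, so none suspends. The rate within the cohort is 1/3, twice the limit. Because the rule is checked throughout, the first, second and third events must be counted no earlier than the 6th, 12th and 18th treated patient.
- Twelve event-free unirradiated patients first: 2 of 2 gives 2/14 = 14.3%, no suspension. 3 of 6 gives 3/18 = 1/6, no suspension; but 3/15, 3/16 and 3/17 (20.0% to 17.6%) would suspend. With immediate events, 10 of the 20 possible orderings of 3 events among 6 patients escape: those with the third event in the sixth patient.
- Four events are tolerated only at 4/24, when accrual is complete; 4/23 suspends.
- The rule is strict early: one event in the first 5 patients suspends (1/5 > 1/6).

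**Step 2: a cohort trigger.** Add: pause cohort c when its events e_c ≥ 2 and 6·e_c > n_c, where n_c is the number treated in it. Since 2/11 > 1/6 and 2/12 = 1/6, this is the second event in a cohort unless it falls in the twelfth patient.

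**Step 3: chance of suspension.** An exact recursion carries the joint probability of (treated, events) in each cohort, multiplies by p or 1 − p for each new patient, and applies the rules after each patient. Events are taken as known before the next patient is treated. The re-irradiated rate is 30%.

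Hand check, unirradiated cohort first with rate 0:

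- Pooled rule: at least 4 events in the first 11 re-irradiated patients, or exactly 3 in the first 5 and none in the next 6. This is 0.4304 + 0.1323 × 0.7^6 = 0.4304 + 0.0156 = 0.446.
- With the cohort trigger: at least 2 events in the first 11, 1 − 0.7^11 − 11 × 0.3 × 0.7^10 = 1 − 0.0198 − 0.0932 = 0.887.

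| Accrual order | Unirradiated rate 0 | 5% | 10% | Fewer re-irradiated patients treated (0 / 5 / 10%) |
|---|---|---|---|---|
| Alternating, unirradiated first in pair | 70% → 90% | 79% → 92.5% | 86% → 95% | 0.9 / 0.6 / 0.4 |
| Alternating, re-irradiated first in pair | 79% → 91% | 85% → 93% | 89% → 95% | 0.5 / 0.3 / 0.2 |
| Unirradiated cohort first | 45% → 89% | 64% → 92% | 78% → 94% | 3.7 / 2.2 / 1.3 |
| Re-irradiated cohort first | 93% → 93% | 93.5% → 94% | 94% → 95% | 0 / 0 / 0 |

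Each cell shows the pooled rule alone, then with the cohort trigger. The last column counts every suspension as final.

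**Sensitivity**, alternating with unirradiated first in pair, unirradiated rate 0 and 5%: a re-irradiated rate of 25% gives 59% → 83% and 71% → 87%; 40% gives 86% → 97.5% and 91% → 98%. If events become known only after 3 further patients (20,000 simulations, 30% rate), the figures are 57-67% → 86-88% alternating and 20-40% → 75-78% unirradiated cohort first.

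**Step 4: false alarms and lost enrolment.** With the same true rate in both cohorts, the chance of at least one suspension rises from 26% to 33% at 5%, 52% to 64% at 10%, and 64% to 75% at 12.5%. A literal cohort 1/6 rule without the two-event minimum would give 44% at 5% and 73% at 10%.

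If every suspension were permanent, with rates of 15% re-irradiated and 5% unirradiated, the chance that the re-irradiated cohort reaches the 10 patients used in 11.3.2 falls from 52% to 42% (alternating, unirradiated first in pair) or 67% to 45% (unirradiated cohort first).

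**The case against.** The strongest reply is that a single study-wide trigger is a defensible choice in a pilot of at most 24 patients, and that people, not only rules, watch the cohorts. Grade 3-5 events must be reported whether or not expected, and SAE reports are due within 48 hours (6.9.3). The DSMC sees SAEs monthly with source documents, and nothing stops it acting on one cohort. With completion expected in three to five years, 24 patients means about 5 to 8 a year, slow enough for case-by-case review. All of that stands. It limits the harm, but gives the DSMC neither a cohort boundary nor a cohort table.

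The assumed rates can also be challenged. Section 1.4 reports no acute or late complications in 13 meningioma patients given similar implants. The upper 95% bound for 0 of 13 is 1 − 0.05^(1/13) = 20.6% one-sided, or 1 − 0.025^(1/13) = 24.7% two-sided, below the 30% used here. The series is indirect: it concerns another tumour, and prior radiotherapy is not described. It neither establishes nor excludes a high rate in re-irradiated patients. The implant risks in Appendix VII ("Hemorrhage, cerebral spinal fluid leak, neurological deficits") are shared by both cohorts, which is why unirradiated rates up to 10% are shown; the gain shrinks as that rate rises.

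The trigger is also sensitive. Taken alone it pauses a cohort with probability 30% at a true 10% rate (1 − 0.9^11 − 11 × 0.1 × 0.9^10) and 51% at 15%, both below 1/6. That stands, and is why the pause must lead to review.

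A reader might infer that half of the first 6 re-irradiated patients could routinely have severe events unnoticed. The documents do not support that. It needs all 12 unirradiated patients first and event-free, and the third event counted no earlier than the 18th treated patient. Nothing sequences the cohorts; under alternation 3 of 6 gives 3/12 and suspends.

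**Conclusion.** The concern holds in a limited form. The only numeric toxicity trigger pools two cohorts that the plan sizes separately, so a one-third rate of severe related events among re-irradiated patients can leave enrolment open under ordinary alternating accrual. That is arithmetic and needs no assumed rate.

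The size of the benefit does rest on assumptions: a 30% re-irradiated rate, 0-10% unirradiated, and prompt knowledge of events. On these, the gain is under one re-irradiated patient when the cohorts alternate, 1.3-3.7 when the unirradiated cohort enrols first, and nothing material when the re-irradiated cohort enrols first. The main gain is that protection depends much less on enrolment order: at unirradiated rates of 0-5%, the pooled rule alone suspends in 45% to 93% of trials by order, against 89% to 94% with the added trigger.

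A reader might go on to infer that re-irradiated patients are shown to be at higher risk, that the 50 Gy organ limits are wrong, or that the design is invalid. The documents support none of these: they give no toxicity rate by prior radiotherapy, and the absence of a cohort boundary does not affect the validity of the response analysis.

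**What to change.** Keep the pooled rule in 11.3.3 and add one sentence: enrolment to a cohort is paused for DSMC review, with possible reopening, when at least 2 patients in that cohort, and more than 1/6 of those treated in it, have a related or possibly related grade 4-5 event. State that the pause is not automatic closure. In 11.5.1.1, require toxicity frequency and severity by cohort. Dose and organ limits need no change.

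This takes one sentence and one split table, with no extra patients or visits. The price is more pauses when the cohorts do not differ, as in Step 4. Even if all suspensions were permanent, at equal rates of 5% to 12.5% mean total enrolment would fall by only 0.2 to 0.5 patients (at 10%, alternating: 14.1 to 13.7). When the re-irradiated rate is higher but still below 1/6, permanent closure would noticeably reduce the chance of that cohort reaching 10 patients. The protocol should say so and leave reopening to the DSMC.

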11.4 Patient Accrual and Study Duration

11.4.1 It is expected that it will take approximately three to five years to complete the study. The analysis for tumor shrinkage will be carried out after each follow-up and collectively after each patient has had 365 days (i.e., 12 months) of follow-up. Study-related data will be stored for 5 years after termination of the study when accrual is no longer taking place and all patients have discontinued follow-up procedures. Blood drawn for translation research will be kept indefinitely or until exhausted.

11.5 Analysis Plan

11.5.1 Interim Reports

11.5.1.1 Interim reports will be updated at least every six months until the results of the study are published. In general, the interim reports will contain information about patient accrual rate with projected completion dates of the trial, status of QA review and compliance rate of treatment per protocol, and the frequencies and severity of toxicity.

11.5.1.2 *The Analysis of Tumor Shrinkage:* This analysis will be carried out when each patient has had at least 730 days (i.e., 24 months) of follow-up. The percent change in size and volume of the adenoma will then be calculated by subtracting the post-treatment measurements from the pre-treatment measurements then divided by the pre-treatment measurements and then multiplied by 100. The mean, median and standard deviation of the percent change will be determined.

11.5.1.3 *Estimation of Secondary Endpoints Related to the Efficacy:* Cumulative incidence approach will be used to estimate the progression free survival. For any individual patient, progressive disease (PD) within the treated lesion will be scored as PD for that patient

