## 11 STATISTICAL CONSIDERATIONS

### 11.1 Primary Endpoint

11.1.1 The primary endpoint of this study is to determine the rate of partial (>30% reduction in GTV) or complete responses occurring within one year of therapy. This will be assessed by measuring the adenoma in three dimensions, as well as determining the total volume, on pre-treatment and follow-up imaging studies. The percent change in size and volume of the adenoma will then be calculated by subtracting the post-treatment measurements from the pre-treatment measurements then divided by the pre-treatment measurements and then multiplied by 100. The mean, median and standard deviation of the percent change will be determined.

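### The primary response rate has no prescribed test, cut-off or evaluable set, and its response window and analysis date conflict

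*Combined protocol and SAP*

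**What the plan says.** Section 11.1.1 makes the endpoint a proportion: "to determine the rate of partial (>30% reduction in GTV) or complete responses occurring within one year of therapy". The calculation that follows is of a different kind: "The percent change in size and volume of the adenoma will then be calculated", and then "The mean, median and standard deviation of the percent change will be determined". Section 11.5.1.2, the only tumour-shrinkage analysis in the Analysis Plan, repeats this calculation. It sits under the heading Interim Reports.

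Section 11.3.2 implies a hypothesis test of the rate. A true rate of 10% or less is not worth pursuing, 50% or more is, and "a sample size of 10 patients will provide 87% power to detect a significantly higher RTS than 10% with an alpha level of 0.025". Up to 12 patients per cohort are enrolled, "allowing for a small number of patients who would be lost to follow-up or otherwise found non evaluable". The same derivation applies to both cohorts.

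Two pairs of statements disagree:

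- **Window.** Sections 2.1.1 and 11.1.1 count a response occurring within 12 months or one year. Section 11.3.2 bases the sample size on the "response rate (PR+CR) of treated subjects at a follow-up interval of 12 months".
- **Analysis date.** Under 11.4.1 the shrinkage analysis "will be carried out after each follow-up and collectively after each patient has had 365 days (i.e., 12 months) of follow-up". Under 11.5.1.2, "This analysis will be carried out when each patient has had at least 730 days (i.e., 24 months) of follow-up".

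**The concern.** A mean, median and standard deviation of percent change cannot show whether a response rate exceeds 10%. Responders can be counted from the patient-level changes, but the rule that turns the count into a conclusion is not written down. No test is named, no number of responders is set and no interval is specified. Section 11.3.2 gives loss to follow-up as one reason for being non-evaluable and leaves the rest open. The 10% and 50% figures are design rates; they do not say how to read an observed 3 of 10 or 4 of 12.

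Section 11.4.1 also has shrinkage analysed after every follow-up, so results will be seen while these choices are still open. With 10 to 12 patients per cohort, the denominator or the window can decide whether a cohort counts as a success.

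**Working it through.** **Inputs.** From 11.3.2: null rate 0.10, alternative 0.50, alpha 0.025, 10 evaluable and up to 12 enrolled per cohort, stated power 87%. From 9.1.1.2: MRI every 3 months for two years, so four scans (3, 6, 9 and 12 months) fall by month 12 and eight by month 24. The protocol gives no cut-off; those below are derived here.

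**1. The plan's own figure.** For an exact one-sided test the type I error of the rule *r or more of n* is P(X ≥ r | n, 0.10).

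- P(X ≥ 4 | 10) = 1 − (0.3487 + 0.3874 + 0.1937 + 0.0574) = 0.0128
- P(X ≥ 3 | 10) = 0.0702, above 0.025

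The cut-off at n = 10 is therefore 4. Power at 50% is 1 − (1 + 10 + 45 + 120)/1024 = 848/1024 = 82.8%, which is 4.2 points below 87%.

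Normal approximation: the null standard error is √(0.1 × 0.9/10) = 0.0949 and the alternative standard error is √(0.25/10) = 0.1581.

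- One-sided 0.025 with continuity correction: (0.4 − 1.960 × 0.0949 − 0.05)/0.1581 = 1.04, power 85.0%
- Two-sided 0.025 without correction: (0.4 − 2.241 × 0.0949)/0.1581 = 1.19, power 88.2%
- One-sided 0.025 without correction: 91.2%

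None of these gives 87% itself. The two nearest differ in sidedness and correction, so the stated power does not reveal which test was meant.

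**2. Denominator.** Suppose four patients respond.

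- Of 10 evaluable: p = 0.0128, passes; Clopper-Pearson 95% interval 12.2% to 73.8%
- Of all 12 enrolled: p = 1 − (0.2824 + 0.3766 + 0.2301 + 0.0852) = 0.0256, fails; interval 9.9% to 65.1%

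The protocol itself plans for 12 enrolled and 10 evaluable, so this case lies within its own expectations.

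**3. Window.** Suppose four of 10 respond by month 9 and one has regrown by the 12-month scan. Counting within 12 months gives 4/10 (p = 0.0128, passes). Counting at 12 months gives 3/10 (p = 0.070, fails; interval 6.7% to 65.2%). Counting within 12 months can never give the lower number.

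**4. Cut-offs for each plausible evaluable number** (exact one-sided test, alpha 0.025).

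| Evaluable n | Cut-off | Type I error | Type I error with one responder fewer | Power at 50% |
|---|---|---|---|---|
| 8 | 4 | 0.0050 | 0.0381 | 163/256 = 63.7% |
| 9 | 4 | 0.0083 | 0.0530 | 382/512 = 74.6% |
| 10 | 4 | 0.0128 | 0.0702 | 848/1024 = 82.8% |
| 11 | 4 | 0.0185 | 0.0896 | 1816/2048 = 88.7% |
| 12 | 5 | 0.0043 | 0.0256 | 3302/4096 = 80.6% |

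(For n = 8, P(X ≥ 3) = 1 − (0.4305 + 0.3826 + 0.1488) = 0.0381.) Power falls from 11 to 12 patients because the cut-off rises from 4 to 5.

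**5. Analysis date.** Running the analysis at 730 days need not change a count confined to the first 12 months. The problem is that 11.5.1.2 does not say which of the eight scans supplies the post-treatment measurement.

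**The case against.** The best reply is that 11.1.1 does prescribe the rate, so nobody would have to infer it from a mean and standard deviation. The phrase about a significantly higher rate points to a one-sided test. Two of three passages agree on the window, and the wording in 11.3.2 can be read as a 12-month follow-up period. The regrowth example is hypothetical, since the documents give no rate of regrowth. The study is a single-arm Phase II pilot that decides only whether further work is justified.

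Much of this stands. It narrows the point but leaves the missing test and cut-off, the undefined evaluable set and the two analysis dates in place. The denominator example needs neither regrowth nor a two-sided test.

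A reader might go further in four ways that the documents do not support:

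- **That sidedness flips the result.** Four of 10 fails at a two-sided 0.025 only if the tail is doubled (2 × 0.0128 = 0.0256). Under the minimum-likelihood two-sided exact test, P(X = 0) = 0.349 exceeds P(X = 4), so the lower tail adds nothing and p stays at 0.0128.
- **That response might be judged on diameters.** Section 2.1.1 defines it by tumour volume and 11.1.1 by GTV, which is also a volume. Diameters enter only as further summaries.
- **That the CT-based GTV outline or the threshold wording is a major conflict.** Section 6.4.1.1 allows CT fused with other imaging. The 30% in 2.1.1 and the strict inequality in 11.1.1 differ only at exact equality.
- **That 87% is a proven error.** It is not reproduced by the exact test, but some approximations come within 2 points.

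**Conclusion.** The point holds. The protocol sizes each cohort for a test of the PR+CR rate against 10%, but prescribes only descriptive summaries of percent change. It also gives two response windows and two analysis dates, and does not define who is evaluable. These gaps can reverse a cohort's conclusion: 4/10 passes, while 4/12 and 3/10 do not. Exact one-sided power is 82.8% at the planned 10 evaluable patients, and between 80.6% and 88.7% for 10 to 12.

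This rests on reading alpha 0.025 as one-sided, on an exact binomial test and on design rates of 10% and 50%. The window example also assumes one lost response. It would be too strong to say that the rate would go unreported or that the later date by itself alters the 12-month result. The gap lies in the decision rule for the primary endpoint and should be closed before the data are analysed.

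**What to change.** Move 11.5.1.2 out of Interim Reports and replace it along these lines: *Once every patient has reached 12 months, the proportion of evaluable patients in each cohort with a volume-based PR or CR on a scheduled MRI within 12 months of implant is tested against 10% with an exact one-sided binomial test at 0.025 and reported with a Clopper-Pearson 95% interval. Success requires at least 4 responders of 8, 9, 10 or 11 evaluable patients, or 5 of 12.*

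Then:

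- Define evaluable before any analysis. One option for the sponsor to confirm is implanted, with a baseline MRI and at least one follow-up MRI by 12 months. Add a sensitivity analysis of all implanted patients, counting the non-evaluable as non-responders.
- Align 11.3.2 to a response within 12 months, and report the 12-month scan alone as a sensitivity analysis. The sponsor should confirm this window, because one unconfirmed scan then suffices.
- Give the 12-month date in both 11.4.1 and the relocated 11.5.1.2.
- Restate power as 82.8% at n = 10, 88.7% at n = 11 and 80.6% at n = 12.
- Keep the mean, median and standard deviation, the analyses after each follow-up and the 24-month data as descriptive, naming the scan used.
- Use one PR threshold in 2.1.1 and 11.1.1.

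The cost is small text edits and a less favourable stated power. No patients or scans are added, because the 3, 6, 9 and 12-month MRIs are already scheduled.
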